The study design is a cluster-randomized controlled trial randomized by battalion. There are 11 battalions in the population we are targeting at Joint Base Lewis-McChord (JBLM) in Lacey, Washington. Soldiers in each battalion will be randomly assigned to the RESULT intervention or usual practice control condition, ideally after baseline data collection, if possible. The intervention targets mid-level military leadership, namely the Platoon Leadership Team (PLT), usually consisting of a platoon leader (i.e., a junior-level officer) and a platoon sergeant.

Figure 1 depicts the overall study design. To test the effectiveness of the intervention, we will collect data pre- and post- intervention from all soldiers, as well as platoon leaders. The control group will be usual practice, as we have done in most of our prior clinical trials. There are an estimated 5200 soldiers in the Battalions included in the study; we anticipate about 30% will participate with a target sample size of $n = 1560$.

Figure 1. Study Design

The surveys will take approximately 30 minutes to complete and will be completed electronically, using REDCap survey software. Survey participation is voluntary and leadership training is mandatory per the senior command at JBLM. However, any data collected from the leaders during training will be consented or if consent is not given, will not be analyzed.

Baseline data collection with all Soldiers will be conducted within a 2-3 week period, with a follow-up survey 4 months later. The leadership training intervention will begin approximately 3 weeks after the baseline survey is completed, with scheduling occurring over a 3 week period.

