Based on advice received from our partners at JBLM, we determined that it is best to randomize at the battalion level because of the likelihood of contamination effects between intervention and control groups if randomization was conducted at a lower level (e.g., platoon or company). Furthermore, randomizing at the battalion level will provide protection from intervention selection effects that occur in traditional non-equivalent control group quasi-experimental designs. Along with the collection and use of baseline, pre-intervention soldier data for the targeted study outcomes, our proposed approach can go a long way in reducing concerns related to biases that undermine internal validity when it is not feasible to randomize more units by balancing potentially confounding covariates across study conditions (Shadish, Cook & Campbell, 2002).

Timeline

Start date: 15 SEP 2019, anticipated end date: 14 SEP 2022

Activity	YEAR 1				YEAR 2				YEAR 3			
	1	2	3	4	1	2	3	4	1	2	3	4
IRB and HRPO approval												
Formative Information Gathering												
Survey Development												
Coordination/Timeline												
Customization of Intervention												
Baseline survey												
Implement Intervention												
6-month Survey												
Cleaning & Analyzing Data												
Report Findings												
Write Papers/Translation/Dissemination												

Note: Lighter color cells are for contingency planning

The first three quarters will focus on hiring personnel, formative information gathering, regulatory review, protocol creation, and refining our schedule. Coordination and refining the timeline for participant recruitment will occur during the first nine months; however, actual participant recruitment will not happen until after we receive HRPO approval. Intervention activities begin about 3-weeks (intervention group only) after the baseline survey so they co-occur in the same quarter. The follow up survey is 4-months post-baseline. Contingency periods are built in for both the intervention and 6-month survey. Data cleaning begins shortly after the first surveys are administered. The last year of the grant is reserved for translating the intervention to other branches of the military, analysis, writing and dissemination of findings.

5. Study Population

a. Number of Subjects

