For the intervention, approximately 102 Platoon Leadership Teams (PLTs) from 7-8 battalions will be targeted for leadership training and testing of Hypothesis 1. For Service Member participation, based on communications with our JBLM partners, we expect about 30% of the total population ($N=5200$) to participate ($n=1560$) at baseline. In addition, based on both our own experience and on those same communications, we expect about 20% attrition at the second data collection, owing largely to individual change in duty stations, remote training, deployments, etc. Thus, we anticipate 1245 soldiers to participate in the study data collection at baseline and at the 6-month follow-up for Hypotheses 2, 3 and 4.

We will work with command teams to avoid data collection, when possible, that would be timed during large deployments or other similar anticipated events. Participation in the training is mandatory, though allowing our researchers to use data collected in association with the training (e.g., test scores, reaction) will be consented. However, the increased sample size will allow our team greater flexibility in dealing with these issues should they arise.

b. Inclusion and Exclusion Criteria

The inclusion criteria for soldiers is to be currently serving Active Duty in one of the targeted battalions, and in positions of platoon leader or below. For the leader training, we will target the platoon leaders and platoon sergeants. We will work with senior leadership to identify these individuals.

c. Vulnerable Populations

No individuals who are known to be members of a vulnerable population will be enrolled. We will not identify subjects on whether they are members of a vulnerable population. In other words, we will not collect any information about subjects' status as part of any vulnerable populations, including prisoners, pregnant woman, children, neonates, and/or adults lacking capacity.

d. Setting

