The data for this study will be generated from a randomized controlled trial with all participating leaders and soldiers (in non-support units) within the participating units randomly assigned (by battalion) to either an intervention or usual practice control condition. Standard general linear and generalized linear mixed model approaches for clustered designs (i.e., hierarchical linear models, multilevel models; Murray, 1998; Murray, Varnell, & Blitstein, 2004) will be used for data analysis for Hypotheses 2-4 to account for the clustered nature of the data. As these models are now widely used and understood and are available in numerous statistical software packages, our discussion here on the specifics of these analyses will be brief. For each hypothesis, link functions for these models will be determined by the scaling of each outcome variable. As study implementation (i.e., intervention-related and data collection activities) will occur at the level of the platoon within brigades, platoon-level random effects will be included in these statistical models. The evaluation of Hypothesis 1 will focus on leaders in the intervention condition providing a point estimate and confidence interval for the usefulness of the training and the change in training-related knowledge from pre- to post-training. Hypotheses 2-4 will focus on differences in the key study outcomes between the intervention and usual practice conditions for soldiers. For these latter models, we will use the outcome variable at baseline as a predictor in the model to adjust for unexpected imbalance across conditions and to increase the statistical power for and precision of parameter estimates (cf. Bodner & Bliese, 2018). Finally based on planned preliminary data analyses, the recruitment wave (i.e., block), rank, gender, unit type, marital status, and mental health symptoms of soldiers may be used as predictors in the statistical models to further increase statistical power or eliminate potential intervention effect bias. Of interest in these latter models is the direction, magnitude, and statistical significance of the parameter corresponding to the intervention condition indicator. As needed, depending on attrition and missing data, this basic generalized linear mixed model will be extended in the analysis of the study hypotheses as mentioned below (e.g., multiple imputation for missing predictor variable values, FIML estimation for missing outcome variable values).

b. Power Analyses

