This section documents the power analyses we conducted for the planned analyses for Hypotheses 1-4.

Key factors for the power analysis are the likely size of the intervention effect and the degree of non-independence, quantified as an intra-class correlation, as leaders and soldiers are nested in platoons, given the expected number of platoons discussed above. Prior research with platoon-level implementation (e.g., Adler, et al., 2009; Adler, et al., 2015a; Adler, et al., 2015b) indicates platoon-level random effects are often considered small in size (e.g., ICCs $< .04$, except when the outcome involves a platoon-level construct such as cohesion). Although small, it is important to include these effects in the analysis models for the study hypotheses and to incorporate these random effects into the power analyses for the study hypotheses. In the power analyses, we assumed an ICC of .04 for the platoon-level random effects.

Hypothesis 1 assesses the perceived usefulness of the training as rated by the leaders that participate in the training. Our prior research involving similar leadership training (i.e., SERVe) indicated that 81% of the 928 trained leaders rated it as good or excellent and 95% rated it as useful to extremely useful for their work. Hypothesis 1 also assesses the increase in leader knowledge of the training material. Prior research indicates that these increases in knowledge are large [e.g., $d = 3.31$ in Anger, et al., unpublished; $d = 1.23$ in [name], et al. (2011)]. Using

the smaller of these effect size estimates for the power analysis for H1, we estimate power to be .99 in the current study.

Hypothesis 2 assesses the effect of the intervention on the soldiers' perceptions of their leaders on the targeted intervention behaviors. Estimates of the effect of similar leadership interventions on subordinate perceptions of targeted leadership behaviors indicate small positive effects [e.g., $d = .27$ in Crain, et al. (2018); $d = .39$ in Odle-Dusseau, et al. (2016)]. Using the smaller of these effect size estimates for the power analysis for H2, we estimate power to be .96 in the current study.

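### Battalions are randomised, but the H2-H4 models and the power section name only platoon clustering, so any battalion variance left after adjustment pushes type I error above its nominal level

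*Combined protocol and SAP*

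**What the plan says.** Section 4 (Study Design) states: "The study design is a cluster-randomized controlled trial randomized by battalion. There are 11 battalions in the population we are targeting". Its Randomization subsection gives the reason: "it is best to randomize at the battalion level because of the likelihood of contamination effects". Section 8a repeats that participants are "randomly assigned (by battalion) to either an intervention or usual practice control condition".

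The only random effect that section 8a names for Hypotheses 2-4 is the platoon. The reason given is that implementation and data collection "will occur at the level of the platoon within brigades, platoon-level random effects will be included in these statistical models". That describes where the work is done, not what was randomised. Section 8a also says "we will use the outcome variable at baseline as a predictor in the model". Recruitment wave, unit type and some soldier characteristics are listed only as possible further predictors.

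Section 8b says: "In the power analyses, we assumed an ICC of .04 for the platoon-level random effects". It takes the cluster count as "given the expected number of platoons discussed above". The only earlier count is in section 5a: "approximately 102 Platoon Leadership Teams (PLTs) from 7-8 battalions will be targeted for leadership training". Section 8b reports power of .96 (H2), .80 (H3) and .84 (H4) and concludes that power is adequate for all four hypotheses.

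No battalion random effect, battalion ICC, battalion-based degrees of freedom, robust variance or permutation test appears. The nearest text is generic: a reference to mixed models for clustered designs with group-randomised-trial citations (8a), and an intention to nest data in units (7b).

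**The concern.** Every soldier in a battalion has the same assignment. A difference between battalions that has nothing to do with RESULT, such as command climate, training cycle or survey follow-up, therefore passes straight into the contrast between arms. A platoon-only model sees 100 or more platoons and treats them as independent replicates, although at most 11 units were randomised. It has no term through which between-battalion variation can widen the standard error.

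This affects the interval and p-value of the intervention indicator in every H2-H4 model, that is, every between-arm comparison in the trial. A chance difference between a few battalions could be reported as an effect of the training, in a study meant to support its extension to other branches and first responders. The power statement has the same gap: it assumes nothing about the level that was randomised.

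**Working it through.** **Inputs from the protocol.** 11 battalions (section 4); N = 1245 with both surveys, and about 102 leadership teams from 7-8 battalions (5a); platoon ICC .04 and d = .27, .205 and .217 for H2, H3 and H4 (8b).

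**Assumed, because not stated.** Two-sided 5%. Split 8:3 or 7:4, reading the 7-8 battalions as the intervention arm. Total platoons J = 102 × 11/8 ≈ 140, or 102 × 11/7 ≈ 160, or 102 if that figure is the total. The total ICC is held at .04, and the battalion ICC (rb) is carved out of it.

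**1. The stated power.** With platoon clustering only, J = 140 and 8:3: m = 1245/140 = 8.89 soldiers per platoon; design effect 1 + (8.89 − 1) × .04 = 1.316; effective N = 1245/1.316 = 946; SE = √[(1/946)(11/8 + 11/3)] = .0730. Normal-theory power is .959/.802/.844, against the stated .96/.80/.84. This fits a calculation without a battalion term but does not prove one. Platoon ICC .04 plus battalion ICC .0045, with baseline correlations of .6 (individual) and .7 (cluster) and 9 df, gives .956/.798/.840.

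**2. What the platoon-only model misses.** With J = 140, the true variance of a battalion mean is rb + (.04 − rb)/(140/11) + .96/(1245/11).

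- At rb = 0: 0 + .00314 + .00848 = .01162.
- At rb = .01: .01 + .00236 + .00848 = .02084.

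The variance among platoon means pooled within arm, which the platoon-only test uses, has expectation equivalent to .01149 at rb = .01. The true variance is .02084/.01149 = 1.81 times that. A nominal 1.96 threshold then acts as 1.96/√1.81 = 1.46, for a two-sided error of about 14.5%.

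**3. Simulated type I error at nominal 5%.** The unadjusted column covers J = 102/140/160 with 8:3 and 7:4 (40,000 trials per cell). The adjusted column uses a soldier-level platoon-intercept model with J = 140, 8:3, individual baseline correlation .6, and cluster baseline correlation .9 to .6 (10,000 trials per cell).

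| Battalion ICC | Platoon-only, unadjusted | Platoon-only, baseline-adjusted |
|---|---|---|
| 0 | .049-.051 | .047-.053 |
| .001 | .057-.060 | .052-.063 |
| .004 | .081-.091 | .069-.088 |
| .01 | .133-.149 | .094-.139 |
| .02 | .209-.233 | .140-.230 |

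A t-test on battalion means with 9 df stays at .047-.052 unadjusted and .047-.055 adjusted.

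**4. Power at the battalion level.** The variance of an adjusted battalion mean is rb(1 − rc²) + (.04 − rb)(1 − rc²)/(J/11) + .96(1 − ri²)/113.2, where ri and rc are the individual and cluster baseline correlations. It is multiplied by (1/8 + 1/3), and power comes from the noncentral t on 9 df. Example with rb = .01, ri = rc = .6, J = 140: .0064 + .00151 + .00543 = .01334; SE = √(.01334 × .4583) = .0782; power .866/.647/.696.

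| Battalion ICC | H2/H3/H4 power, rc .6 | H2/H3/H4 power, rc .9 |
|---|---|---|
| 0 | .983/.877/.910 | .995/.933/.955 |
| .004 | .947/.777/.821 | .990/.906/.934 |
| .01 | .866/.647/.696 | .979/.862/.897 |
| .02 | .726/.496/.541 | .952/.788/.831 |

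For J = 140 and 8:3, power drops below the stated values once rb exceeds about .003 (rc .6), .008 (rc .8) or .018 (rc .9). Across the other layouts (J = 102, 8:3; J = 160, 7:4) the crossing point runs from .0015 to .0277. Without the baseline covariate, which is not the planned analysis, J = 140 and 8:3 gives .91/.71/.75 at rb = 0 and .69/.47/.51 at .01.

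**The case against.** **The plan is brief rather than wrong.** Section 8a cites group-randomised-trial methods, says its account is short, and does not state that platoon is the only random effect. Wave and unit type might absorb some battalion differences. However, the one sentence that fixes a level names the platoon and gives a reason unrelated to randomisation, and the optional covariates are not a commitment. An analyst following the text would fit a platoon-only model.

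**The size is assumed.** This is correct. At battalion ICC .001 the adjusted error is only .052-.063. The highest figures need .02, half of an ICC that section 8b presents as near the top of the usual range. Only the direction is established. But the plan gives no ground for taking battalion variance as zero, and section 8b itself argues that small cluster effects should be modelled.

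**The power criticism is weak.** In part. With the planned baseline covariate and no battalion variance, 9-df power exceeds the stated figures. The objection to the power claim is that it lacks support, not that it is false.

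**The 5% result belongs to a different test.** This also stands. The error rates and power quoted for 9 df describe the battalion-mean test. A mixed model with a non-negative battalion variance, tested on 9 df, is conservative at small ICCs: simulated error is about .02-.03 at battalion ICC 0 to .004. Its unadjusted H2/H3/H4 power at ICC 0 is about .89-.90/.64-.66/.70-.71, against .91/.71/.75 for battalion means. It keeps error at or below nominal, at some cost in power.

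**Eleven is the number targeted.** The number finally randomised is not given, so the degrees of freedom should follow the battalions analysed.

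**Conclusion.** The concern holds, and the plan must be changed. The H2-H4 analysis as written omits the level that was randomised. For any outcome with battalion variance left after adjustment, the platoon-only test exceeds its nominal error rate. If that residual variance is zero, the test is sound, but nothing in the protocol supports assuming so.

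Confidence is high in the omission and its direction. The degree of inflation is conditional on the assumptions listed, including equal platoon sizes and continuous outcomes in the simulations. At a battalion ICC of .01, it is roughly two to three times nominal. The statement of adequate power is unsupported until a battalion ICC and a baseline correlation are given.

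**What to change.** **Section 8a.** Specify random intercepts for battalion and for platoon within battalion, and keep the battalion term even if its variance is estimated at zero. Fix in advance a small-cluster test of the intervention indicator, for example between-battalion degrees of freedom equal to battalions analysed minus 2 (9 if all 11), less one per battalion-level covariate. If an error rate close to 5% at small ICCs is wanted, a t-test on baseline-adjusted battalion means is the alternative. A battalion-level permutation test is an optional sensitivity check.

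**Section 8b.** State alpha and sidedness, total platoons, allocation, an assumed battalion ICC with a range, and the assumed baseline correlation. Recompute H2-H4 power at the battalion level for the test chosen, and revise the adequacy sentence to match.

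**Cost.** Some wording, one extra random effect and a rewritten set of power figures. Soldiers already report their unit (5e, 7b), so no new data are needed. The price is wider intervals and possibly lower stated power, depending on the battalion ICC and on how well baseline predicts follow-up.

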Specific Aim 3: To test the effects of the RESULT training compared to the control group on perceptions of increased leadership resilience-supportive behaviors from the perspective of the service members, following the training (Hypothesis 2).

Specific Aim 4: To test the effects of the RESULT training compared to the control group on behavioral health measures such as emotion regulation, connectedness, team cohesion, psychological health, and physical health following the training (Hypotheses 3 & 4).

Specific Aim 5: Translate the tenets of the RESULT to other branches of services, and other employee populations who would benefit, such as first responders.

Study Hypotheses

- 1) Leaders in the intervention group will report positive reactions to the training and will demonstrate increased knowledge from pre-test to post-test.
- 2) Service Members in the intervention group will report improved perceptions of resilience-supportive leadership behaviors compared to those in the control group.
- 3) Service Members in the intervention group will report higher levels of resilience-related factors such as adaptive emotion regulation strategies, resilience, social connectedness and belongingness, and team cohesion, compared to those in the control group.
- 4) Service Members in the intervention group will report higher levels of resilience-related outcomes such as psychological and physical health and well-being, compared to those in the control group.

3. Background

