All study staff dealing with both participants and/or data will have completed sanctioned Human Subject Research training. The PI and Project Manager both have experience with DoD-regulated research and reviewed these regulations with the DoD Science Officer after the grant was awarded. They will both be responsible for training any new study staff with regard to these specific DoD regulations.

b. Survey Measures

We will collect sociodemographic data and military experience, including military work history, combat exposure and deployment history. Our survey outcome measures will map on to our hypotheses to ensure we can evaluate between- and within-group effects. We will also ask which specific unit to which they are currently assigned so we can nest data within units and account for unit-level similarities (see Statistical Analysis below). Some of the hypotheses include data that are not from the surveys, such as training data (pre- and post-tests) (see Hypothesis 1), but we will track that information as well and merge with survey data. Table 1 includes a summary of proposed measures, sources, and when and from whom they will be collected. All proposed measures have been used in previous research and are psychometrically sound. A list of individual surveys items are included in our submission.

Hypothesis 2 will be evaluated with a measure assessing the leader's support for resilience within their unit. This measure, commensurate with previous work we have done (e.g., Family-Supportive Supervisor Behaviors and Sleep Leadership), will be developed based on tenets of the intervention. It will be measured from the perspective of the subordinates (e.g., "My platoon leadership team supports resilience in our unit"). Before reporting any

findings on Hypothesis 2, we will examine the psychometric properties of the adapted measure to ensure reliability and validity.

The bulk of the survey will be comprised of measures that assess Hypotheses 3 and 4. Hypothesis 3 is specific to perceptions around resilience factors such as social connectedness, resilience, and emotional regulation, whereas Hypothesis 4 is specific to perceptions around resilience-related outcomes including psychological, physical health, and well-being.

Table 1. Summary of Survey Measures

Concept	Measure	Reference	# of Items	When collected*	Who*	Hyp.
Leader Training Data	Leader reactions to training	Adapted from [name] et al. (2011)	3	T	PLT	1

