Hypothesis 3 assesses the effect of the intervention on the soldiers' resilience-related factors such as adaptive emotion regulation strategies, resilience, social connectedness and belongingness. . Estimates of the effect of similar interventions on adaptive emotion regulation vary widely [e.g., $d = .26$ in Bentley, et al. (2018); $d = .30$ in Cameron, Carroll & Hamilton (2018); and $d = .90$ in Mahatmya, Thurston, & Lynch (2018)]. Estimates of the effect of similar interventions on prosocial connections tend to be small in size [e.g., $d = .205$ for organizational citizenship behaviors in [name], et al. (2016)]. Using the smallest of these effect size estimates for the power analysis for H3, we estimate power to be .80 in the current study.

Hypothesis 4 assesses the effect of the intervention on the soldiers' resilience-related outcomes such as psychological and physical health and well-being. Estimates of the effect of similar interventions on health outcomes tend to be small in size [e.g., $d = .26$ for physical health in [name], et al. (2011); $d = -.217$ for blood pressure in [name], et al. (2015)]. Using the smallest of these effect size estimates for the power analysis for H4, we estimate power to be .84 in the current study.

In summary, based on the expected sample sizes, participation and attrition rates, and effect sizes (i.e., from the research literature) we are adequately powered to test the 4 study hypotheses.

c. Missing Data and the Application of Intent-to-Treat

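### Section 8b exempts cohesion from the small platoon ICC and then powers every hypothesis at .04, so the stated .80/.84 does not carry over to unit cohesion and the .96 for H2 is uncertain

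*Combined protocol and SAP*

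**What the plan says.** Section 8b (Power Analyses) describes platoon-level ICCs in earlier platoon-based research as small, often below .04, "except when the outcome involves a platoon-level construct such as cohesion". Shortly afterwards it fixes the planning value: "In the power analyses, we assumed an ICC of .04 for the platoon-level random effects". No other ICC appears in the document.

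For H2 the section takes d = .27: "Using the smaller of these effect size estimates for the power analysis for H2, we estimate power to be .96 in the current study". For H3 it takes d = .205 and states power of .80; for H4 it takes an absolute d of .217 and states .84. The closing summary says that power is adequate for all four hypotheses.

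Cohesion is among the outcomes. In section 2, H3 ends with "social connectedness and belongingness, and team cohesion, compared to those in the control group". Table 1 (section 7b) lists an eight-item Unit Cohesion scale but labels it Hyp. 4. The H3 power paragraph leaves cohesion out of its list, and no power figure is given for cohesion by itself.

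H2 is measured by soldiers' ratings of their leaders. The sample item in section 7b is "My platoon leadership team supports resilience in our unit".

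**The concern.** The sentence that justifies .04 also says where it does not apply, and the power analysis makes no allowance for that exception. A higher ICC inflates the design effect and lowers power. For cohesion the H3 and H4 figures are therefore too favourable on the protocol's own reasoning, and the blanket summary is not supported for that outcome.

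The same question arises for H2. Cohesion is given as an example of a platoon-level construct, not as the only one, and the soldiers in a platoon all rate one leadership team. H2 also carries the highest stated power of the soldier-level hypotheses.

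What is at stake is the reading of a null result. If cohesion or leader-behaviour ratings show no significant difference, stated power of .80 to .96 invites the conclusion that the training has no effect, when the trial may have had a much weaker chance of detecting one.

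**Working it through.** **Inputs from the document.** N = 1245 soldiers at follow-up (section 5a). About 102 Platoon Leadership Teams from 7-8 battalions are targeted for training (section 5a), out of 11 battalions (section 4). Effect sizes are .27, .205 and .217, and the platoon ICC is .04 (section 8b).

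**Assumptions.** Alpha is not stated; I use .05 two-sided. The total number of platoons K and the fraction of soldiers in the intervention arm p are not stated either, so I use two readings:
- A: 102 platoons in total, p = 7.5/11 = .682.
- B: 102 trained platoons in 8 of 11 battalions, so K = 102 × 11/8 = 140.25, p = 8/11 = .727.

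**Formulas.** m = N/K; DE = 1 + (m − 1) × ICC; Neff = N/DE; SE = 1/√(Neff × p × (1 − p)) in SD units; power = Φ(d/SE − 1.96).

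**Step 1: reproduce the stated power at ICC .04, with no gain from baseline adjustment.**
- A: m = 12.21; DE = 1 + 11.21 × .04 = 1.448; Neff = 860; SE = 1/√(860 × .2169) = .0732. d/SE = 3.69, 2.80, 2.96, so power is .958, .799, .842.
- B: m = 8.88; DE = 1 + 7.88 × .04 = 1.315; Neff = 947; SE = 1/√(947 × .1983) = .0730. Power is .959, .802, .845.

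The stated values are .96, .80 and .84, so both readings match. Platoon count and allocation trade off in the formula, so other pairs can also fit. A smaller number of platoons split evenly would do so, but it disagrees with about 102 teams and 7-8 of 11 battalions, and I do not use it.

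**Step 2: raise the ICC.** The document gives no value for the exception; .05 to .20 is my assumption. Example for A at ICC .10: DE = 1 + 11.21 × .10 = 2.121; Neff = 587; SE = .0886; .205/.0886 = 2.31; power = .64.

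| Outcome | Layout | ICC .05 | .10 | .15 | .20 |
|---|---|---|---|---|---|
| Cohesion, d = .205 (as H3) | A | .77 | .64 | .54 | .47 |
| | B | .78 | .67 | .59 | .52 |
| Cohesion, d = .217 (as H4) | A | .82 | .69 | .59 | .51 |
| | B | .82 | .72 | .64 | .57 |
| H2, d = .27 | A | .94 | .86 | .77 | .69 |
| | B | .95 | .89 | .82 | .75 |

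**Step 3: where power crosses .80.** Cohesion at d = .205 is already at .80 with ICC .04, so it has no reserve. At d = .217 it crosses at an ICC of about .055 (A) to .061 (B). H2 crosses only at about .135 (A) to .165 (B).

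**Step 4: possible offset.** If the baseline score explains 25% of the outcome variance (assumption, applied to the whole variance), SE is multiplied by √.75 = .866. At ICC .10, cohesion is then .76-.79 (d = .205) or .81-.84 (d = .217), and H2 is .94-.96. At ICC .15, cohesion is .66-.71 or .71-.76.

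These figures follow the plan's own approach, with clustering by platoon only. Clustering by battalion, the unit of randomisation, is a separate matter and is not counted here.

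**The case against.** Four points can fairly be made for the plan.

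First, a reader might infer that the protocol contradicts itself on H2. It does not go that far. Cohesion is the only construct it names, H2 is described as individual soldiers' perceptions, and no ICC for leader ratings is given. Two of the three H2 measures in Table 1 are general ratings of leader effectiveness and supervisor support; the quoted item illustrates only the resilience-support measure. This stands: a higher ICC for H2 is a reasonable inference from the shared target of the ratings, not something the documents show.

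Second, a reader might say that a stated cohesion power is wrong. None is stated. What stands is narrower: the H3 or H4 figure and the closing summary cover cohesion by implication, and that implication fails.

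Third, the size is assumed. An ICC only slightly above .04 also fits the protocol's sentence, and at .05 H2 is still .94-.95 and cohesion at d = .217 is .82. This stands as a limit on the magnitude. At d = .205, however, any real excess over .04 takes cohesion below .80.

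Fourth, section 8a commits to the baseline outcome as a predictor, partly to gain power, and the stated figures reproduce without it. The offset is real but unquantified, because no baseline correlation is given. At 36% of variance explained and ICC .10, cohesion at d = .205 would return to .82 in layout A. At 25% and ICC .15 it would not. That is a reason to state the offset, not to leave the ICC unreconciled.

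**Conclusion.** The point holds for cohesion. The protocol exempts it from the small ICC, plans to test it and then declares power adequate on an ICC of .04 alone. Without baseline gain, cohesion power lies between .77-.78 and .47-.52 at d = .205, or between .82 and .51-.57 at d = .217, as the ICC runs from .05 to .20.

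For H2 the .96 is likely, but not demonstrably, too high. Over the same range it falls from .94-.95 to .69-.75, and H2 keeps at least .80 up to an ICC of about .135 to .165. The documents do not support a claim that H2 is underpowered, nor a definite shortfall for cohesion once baseline adjustment is credited.

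The conclusion rests on an assumed two-sided .05, on platoon counts and allocations inferred from sections 4 and 5a, and on an ICC range that has no source in the document. That .04 underlies the stated figures does not rest on the range: the plan says so, and .96/.80/.84 reproduce at that value.

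**What to change.** In section 8b:
- Limit the ICC of .04 to individual-level outcomes.
- Restate power for cohesion over a stated range of ICCs above .04, and give the same range for H2 as a sensitivity analysis.
- State the number of platoons, the allocation, alpha and sidedness, and any baseline correlation credited.
- Qualify the summary on the four hypotheses wherever the restated figures do not support it.

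In section 2 and Table 1, assign cohesion to one hypothesis, so that it is clear which effect size applies.

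The cost is a recalculation and a few sentences. Design, sample and analysis model are unchanged, although the stated power for cohesion, and perhaps for H2, will be less favourable.
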